2.0 Background

Perinatal CNS injuries include brain dysmaturity after preterm birth, global ischemic or arterial stroke, severe intracranial hemorrhage and hydrocephalus, and sequelae of neuroinflammation due to intrauterine infection, maternal diabetes or maternal immune activation.¹⁻⁵ Perinatal CNS injuries have life-long impact via significant disruption of the normal developmental trajectory of neural circuits.^{1,4,5} Abnormal connections, along with decreased populations of myelinating cells and inter-neurons, result in less myelination, fewer brainstem-cortical connections, and reduced corpus callosal and corticospinal tract volume and connections.^{1,3-5} Even with developmental plasticity,⁵ there are frequently significant deficits following perinatal insult.

Many conditions that contribute to perinatal brain injury may not be reliably predicted. Further, evidence-based neuroprotective treatments are very limited and must be delivered shortly before or after delivery.

Therefore, novel rehabilitation approaches that improve infant morbidity are needed.

Motor weakness is frequently the first manifestation in young infants of later significant motor impairments. Standard pediatric rehabilitation programs, such as CIMT, maximize the movement and functional abilities of motor-impaired children through the use of high-dose intensive and child-active rehabilitation strategies.^{6-11,13} Multiple investigations of CIMT show clinically meaningful and sustained benefits with high levels of scientific evidence.¹⁰⁻¹³ While CIMT protocols vary, the most efficacious protocols use dosage between 60-120 treatment hours,^{9,13} within a condensed time period, frequently multi-hour sessions daily for 4 weeks. There is substantial evidence that such intensive therapeutic bursts (e.g., many hours each day on multiple consecutive days across multiple weeks) create opportunities for the development of increased motor and functional skills in infants with early motor delays. Thus, activity-dependent neuroplasticity is reinforced through intense repetition.¹² However, these early intensive therapy models are difficult to accomplish in many households.¹¹

There is evidence that even with significant brain injury, neuromodulation via vagus nerve stimulation (VNS) delivered during a motor task can harness activity-dependent plasticity and lead to improved, near-normal outcomes.¹⁷⁻²⁴ Adjunctive neuromodulation that increases the efficiency of CIMT, might lessen the burden on infants, therapists and parents. Therefore, our premise is that in babies with unilateral motor weakness after perinatal brain injury, brain stimulation via taVNS simultaneously delivered with CIMT will boost motor cortical plasticity involved in motor tasks, with better function in a shorter time.

The data in animals and humans support the premise that both cervically-implanted and transcutaneous auricular VNS paired with motor rehabilitation improve functioning.¹⁸⁻³² In rats, cervically-implanted VNS paired with movement led to a doubling in size of the primary motor cortex associated with the movement.¹⁸ In adult stroke patients, upper extremity Fugl-Meyer scores significant increase with VNS-paired rehabilitation vs rehabilitation alone.²⁵⁻²⁷ An FDA pivotal study of cervical-VNS for adult stroke (NCT03131960)³¹ is reporting clinically and statistically significant functional improvement

with active vs sham VNS paired with rehabilitation. Similar results are being obtained with non-invasive VNS by stimulating the auricular branch of the vagus nerve located in the ear with a transcutaneous electrical nerve stimulation (TENS) device.^{16,17,30-32} An ongoing MUSC COBRE trial is also using taVNS-paired with upper limb rehabilitation in adult stroke patients ([name], PI; NCT 04129242). In infants, TENS devices are FDA-approved for pain management. TENS serves as the basis for the Soterix Medical taVNS unit used in our infant feeding trial and this proposed study. We have conducted safety and feasibility trials of taVNS in infants with oromotor disability due to perinatal brain injury and observed no minor or major adverse effects.^{16,17} Our work validates parameters for delivering taVNS, suggesting that two-minute taVNS periods at 500μs, 25Hz, and slightly less than perceptual threshold (PT) are safe, tolerable and produce changes in white matter microstructure consistent with neuroplasticity in infants.^{16,17,33-35} (see preliminary data)

Activation of afferent vagal fibers in the dorsal nucleus and locus coeruleus along with an associated stimulus, results in secretion of norepinephrine, a high-alert signal that helps activate motor to hippocampal pathways and re-establish normal connections. [name] has shown via fMRI that taVNS also activates key sensorimotor targets in adults, including thalamus and basal ganglia that are also key areas of perinatally acquired CNS injury.³³ We also changes in white matter microstructure consistent with neuroplasticity in infants following taVNS-paired feeding (preliminary data). Thus, a non-invasive taVNS approach may be particularly effective in infants who manifest early motor disabilities due to perinatal brain injury and whose developmental and reparative plasticity is greater than for adults.⁵

We envision that CIMT paired with taVNS may boost neuroplasticity and allow for delivery of intensive therapy at a **minimal dosage of 40h** while improving infant outcomes. Ultimately CIMT pairing with taVNS may be used in the hospital, clinic or home setting to improve motor dysfunction, reduce the incidence or severity of hemiplegic CP, and decrease financial and emotional costs of caring for a child with motor disability. This would significantly improve the quality of life for these children with disabilities. *Importantly, this noninvasive technology may be effective in rehabilitation, even when other neuroprotective treatments are not available, as many conditions leading to motor disorders in infants are unpredictable or unavoidable.* Significance of this pilot proposal is enhanced by the following:

- We will generate pilot data on feasibility and gather data on effect for taVNS in infants getting standard of care CIMT for rehabilitation after perinatally acquired brain injury and stroke.
- A collaborative, innovative multidisciplinary team will execute these proposed studies, including [name] an expert in infant CIMT and taVNS expert ([name]).
- The infant taVNS system for this study allows the therapist to control the delivery of taVNS with the intent of ultimately developing home-based CIMT therapies.

INNOVATION

Application of neuromodulation to perinatally acquired brain injury is innovative. Activity-dependent plasticity that is enhanced by electrical stimulation is just beginning to be translated to infants after perinatal brain injury.^{16,17} CIMT plus transcranial direct current stimulation is being tested by [name] group in older children and adults with cerebral palsy.^{14,15} VNS was pioneered by [name], and non-invasive transcutaneous auricular VNS (taVNS) was developed by Drs. [name] and [name]. With the collaboration of brain stimulation experts, occupational therapists, neuroradiologists, and a neonatal clinical translational investigator, **we are the first to use taVNS in infants and neonates.**^{16,17} In our infants with brain dysmaturity or overt brain injury, we postulated that neuromodulation with non-invasive taVNS may positively influence abnormal circuits to improve neuronal connectivity and neuroplasticity and improve oromotor skills. Importantly, taVNS was well accepted by parents and care providers.

Infant CIMT have been shown to have a positive influence on early motor abilities and hand function,^{13,36-39} but current models continue to require 60-120 hours of intensive therapy, including the recently funded Intensive Infant Rehabilitation (I-ACQUIRE, NCT03910075) Phase III Clinical Trial. These intensive therapy models raise challenges for parents juggling the family's daily schedule.¹¹ Using two innovative and potentially effective therapies in young infants, we aim to decrease the time commitment and improve outcomes.

Overview of Innovation: This proposal will use the following innovative techniques and goals

- A novel, portable, therapist-triggered taVNS system that can be used during CIMT sessions
- A novel cohort of older infants with unilateral weakness who are referred to CIMT therapy
- Safety and feasibility of taVNS paired with CIMT
- Assessment of therapist delivering CIMT with high fidelity using a CIMT fidelity tool¹³

To our knowledge, no other investigators are treating young infants who have perinatally acquired brain injury with CIMT+ taVNS to improve motor skills or developing a similar treatment paradigm.

Preliminary data from pilot trial of taVNS in infant feeding

We have significant experience with taVNS for feeding failure in infants from our pilot trial of taVNS-paired feeding, who were refractory to standard of care early feeding interventions and were slated to receive a G-tube. We obtained IRB approval with medical device designation of non-significant risk for this open-label trial with parental consent.

Inclusion Criteria of previous taVNS feeding trial: Infants born ≤ 33 completed weeks gestation, or with brain injury (HIE); clinically stable; failing oral feeding; clinical team discussing need for G-tube with parents.

Exclusion Criteria of taVNS feeding trial: Cardiomyopathy, significant respiratory support

Primary Efficacy Outcomes: Increase in total daily oral feeding volumes compared before and during treatment, achievement of full oral feeds ($\geq 130\text{ml/kg/d}$ with weight gain), avoiding G-tube.

Secondary Efficacy outcomes: Brain changes measured by diffusion imaging (DKI) in white matter tract (WM) integrity before and after taVNS-paired feeding, normalized for weeks of development. Improvement in overall motor function by Specific Test of Early infant Motor Performance (STEP).⁴⁰

Primary Safety Outcomes: Bradycardia (HR<80bpm for 5 seconds), as potential effect of taVNS on the dorsal nucleus and efferent cardiac vagus nerve fibers; skin irritation; Change >3 points in the Neonatal and Infant Pain scale (NIPS).^{41,42}

Treatment Protocol:

- taVNS pulses delivered via a left ear electrode at 25Hz, pulse width 500 μ seconds.
- Perceptual threshold (PT) determined by increasing current slowly until infant detects tingling with facial change or shrug.
- taVNS delivered at 0.1mA $<$ PT, paired with suck-swallowing during one (n=15) or two (n=18) oral feedings per day, for 2-4 wks.

Fig. 1. Operator-controlled taVNS system: Baby bottle sleeve has a button trigger and wired connection to Soterix taVNS unit, with wired electrode on left tragus, as shown. We deliver taVNS by manual trigger coordinated with visible suck-swallow.

Results:

Efficacy outcomes: To date, 19/35 infants destined for G-tube attained full oral feeds with taVNS paired feedings (54% Responders). taVNS Responders showed a significant increase in mean daily po volumes vs Non-Responders who received G-tube ($p<0.05$). We also demonstrate a dose response with greater increase in slopes of daily po feeding volumes ($F, 8.05, p=0.01$, **Fig. 2A**) and shorter time to full po feeds ($p<0.05$, **Fig. 2B**) in twice vs once daily treatments.

Secondary efficacy outcomes: dMRI before and after taVNS treatment, shows white matter plasticity changes in fractional anisotropy (FA) that are significantly greater for Responders versus Non-Responders in corpus callosum and external capsule, per week of development (**Fig. 3**). Both groups showed greater than normal FA increase, compared with published normal developmental changes (indicated by dashed line).⁴³

Target attainment: Transient HR decrease was reliably demonstrated within 30sec of taVNS onset, with a quick rebound in 60sec. The HR decrease was reproducible within and across individuals. **Fig. 4** shows the consistency of heart rate changes before, at onset of taVNS, and during 1st 5 min of feed over all sessions for one subject. **Fig. 5** shows significantly lower HR during onset of taVNS-paired feeds compared with pre-feed, and no HR change during control feeds without stimulation.

Safety outcomes: We observed no bradycardia (HR<80bpm 5sec) & no skin irritation. Persistent increase in discomfort scores NIPS >3 occurred in 3 of 228 sessions (1.3%) and resolved with decreasing current.

In summary, our first in human neonate and infant pilot trial of taVNS paired with an oromotor task of bottle feeding, using our custom taVNS system, showed safety and feasibility, and achieved encouraging results in >50% of infants slated for G-tube achieving full oral feeds in 2 weeks.^{16,17}

Other Achievements that impact this proposal: We recently received Breakthrough Device designation from the FDA for the BabyStrong device, which is similar to the system proposed in this application. Our phase I STTR early RCT with the BabyStrong system ([name], [name], MUSC FRD Accel), received a favorable score from NICHD STTR study section with notification of probable funding after council review.

Our infant taVNS feeding data,¹⁶⁻¹⁷ our early FDA breakthrough device development for young infants, and other studies indicating positive results of taVNS paired with motor learning in adults,²⁶⁻³² support study of this neuromodulatory technique in infants with significant motor deficits of hemiplegia after perinatally

acquired brain injury.

[figure not shown]
3.0 Intervention to be studied

Proposed Trial of CIMT Paired with taVNS

We will treat up to 10 infants referred for CIMT with one-sided motor weakness to receive active taVNS paired with 40 hours of CIMT. We will perform infant motor assessments before and after the treatment is completed to answer the following questions:

- 1) Is taVNS feasible and safe of in infants 6-18months of age undergoing CIMT therapy?
- 2) Does infant motor ability increase with low-dosage 40h CIMT + active taVNS as measured by: 1) upper extremity motor abilities, 2) gross motor skills, and 3) individual treatment goals.

Experimental set-up: For this proposal we will modify our BabyStrong system, which uses the FDA cleared Soterix taVNS unit, Neolead® electrode in front of the tragus and custom ear electrode for infant sized ears, wired trigger control of stimulation with a trigger button or direct input in the Soterix taVNS unit. We will substitute a portable, therapist-triggered taVNS system with hand held trigger button as seen in **Figure 6**. The therapist will activate a hand-held button for 2min-on/30 sec-off control of stimulation during a CIMT session.

We have an established, collaborative, innovative multidisciplinary team to execute these proposed studies. In addition to MUSC's infant taVNS trial, Drs. [name] and [name] have been collaborating for 10 years on infant developmental assessments and other therapeutic studies. [name] has been an innovator in CIMT in young infants and has investigated modified CIMT approaches in the U.S. and abroad.^{37,45-47} These studies provided evidence of how to modify signature pediatric CIMT approaches, while adhering to the essential elements of the therapy, to assure high levels of treatment efficacy. Pertinent to this trial, she also published the first case report on successful implementation of CIMT in infants under one year of age.³⁷

Working with development, perhaps activating critical motor synapses, taVNS paired with CIMT could deliver groundbreaking innovation in the increasing problem of unilateral motor weakness in infants with perinatally acquired brain injury.

Aim 1. To determine the feasibility and safety of taVNS in 6-18mo infants with unilateral motor weakness undergoing CIMT therapy in an open label pilot trial. The CIMT therapy sessions will be videotaped and a random weekly session (20% sessions) will be scored for CIMT treatment fidelity while the therapist is delivering taVNS. [name] will score these using a CIMT fidelity scoring system previously used in other studies.¹³ Scores that meet or exceed therapist goals indicate that taVNS can be delivered by the therapist while delivering high quality CIMT.

Aim 1 Procedures:

- 1) We will follow the following protocol for CIMT paired with taVNS with one OT therapist delivering CIMT with a brain stimulation research assistant (BSL-RA) supervising the delivery of taVNS:
- 2) Hydrogel electrodes are placed in front of tragus, and inner tragus/cymba chonchae, securing the wires behind head with tape, and placing wire under shirt.
- 3) CIMT and BSL therapists will establish perceptual threshold (PT) daily, increasing +0.1mA, until infant shows signs of tingling sensation.
- 4) We will treat with stimulation at 0.1mA<PT, 500μsec, 25Hz, during each CIMT session.
- 5) The OT therapist delivering CIMT will start stimulation by pushing the button for a continuous 2min-on, 30sec-off program (similar to taVNS-feeding settings^{16,17}), while administering CIMT. Trigger button is off for rest.
- 6) Impedance is constantly displayed on the Soterix unit (*good, moderate or poor*). If contact is *poor*, a beep alerts the therapist and the BSL RA will adjust the electrode to ensure contact and delivery of stimulation.
- 7) Both parent and OT will be queried by weekly questionnaire to assess their perception of ease of use, infant tolerance, general acceptance and any recommendations for improvement of taVNS delivery during the 4 weeks of CIMT therapy.

Table 1. Key Features of Routine Infant CIMT Program

Dosage	Each session will be 2 hours, 5 sessions each week, over 4 consecutive weeks for a total dosage of 40 hours.
Therapy setting	MUSC's pediatric OT lab, fully equipped with mats, benches, toys for pediatric rehabilitation equipment
Type of constraint	We fabricate custom-made hand splint/orthotics for the infant's less-affected hand and place a soft mitt on this splint, as we have used in prior CIMT trials. The constraint mitt will only be worn during the therapy sessions. ³⁶⁻³⁹
Therapist	Highly trained therapists trained in the principles of pediatric CIMT ³⁸ will use immediate and varied reinforcement, primarily verbal praise, smiles, and supportive gestures, to sustain the infant's attention, engagement, and enjoyment, then "shape" a movement by using prompts and increasing the demands for greater precision, strength, fluency (coordination), and speed, using technique of "successive approximations". The therapist implements a "MR3 cycle," of Movement, Reinforcement, Repetition, and Refinement, used in the I-ACQUIRE Phase II clinical trial to progress the child in increments as skills increase
Components of infant CIMT	Sessions will actively engage the infant to initiate, attempt, repeat, practice, and refine a wide range of age developmentally appropriate skills and movements using the more-impaired arm and hand. Emphasis will be on engagement of the infant and the affected upper extremity in age- appropriate activities in positions of supine,

sessions	prone, sitting, quadruped, and supported standing.
Documentation for each session	Therapist will keep formal daily therapy logs and ask mothers to report on activities and progress at each session. Therapist and mothers will jointly review targeted therapy goals at each session.
Discharge program	Therapist and parents develop a practical written plan to maintain gains made during the CIMT program. The plan will involve motor skills and functional activities appropriate for the infant's age at discharge from the program.

Technical administration of taVNS: The therapist will need assistance with learning the taVNS trigger system and integrating it with CIMT. 1) We will provide training sessions for the single designated CIMT therapist who will perform all interventions before enrolling patients, and 2) the BSL RA will supervise and assist with taVNS treatments with each patient session. The brain stimulation RA will be trained to deliver stimulation, place the ear electrode for good impedance readings, and demonstrate this with [name] or [name] prior to supervising the CIMT therapist. We have several RAs who are experienced in infant taVNS who may also supervise any new RAs in the procedures. As part of this training, we have an instructional video for setting up the taVNS system with an infant.

Limitations and alternative approaches: The therapist may provide feedback that a different trigger switch is needed or a different program with a '2min on-30sec-off' loop that does not require pressing the button repeatedly. We will then incorporate this feedback in our next design of the trigger. Previous NIH reviewers of our similar Soterix-based BabyStrong STTR phase I were concerned about overstimulation, requesting a fail-safe stop time for each trigger. We are using the same infant-modified Soterix taVNS unit, and for establishing safety in this CIMT+taVNS pilot we will use the same duty cycle of 2min-on, 30sec-off. For safety the taVNS unit limits deliverable microcurrent is limited to a maximum of 2mA, which is sufficient for adults to register a tingling. Feasibility of using wired ear electrodes: The infant should be engaged during CIMT such that the ear electrode does not irritate the infant. If the first infant does not tolerate the ear electrode, we will train infants on the electrode by having the mother place the electrode on the ear prior to the session and at home, to get the infant used to ignoring the presence of the electrode. The electrode should not impact hearing during the session. In our pilot trial infants received a hearing screen before discharge, all infants passed the screen except one, and that infant failed the hearing screen before taVNS treatment was initiated. No hearing adverse events were noted in that pilot trial.

Feasibility of delivering high fidelity CIMT with taVNS: We expect the therapist to maintain high fidelity of CIMT delivery while delivering taVNS over the weeks of treatment for the first infant. If the BSL RA has to assist in most therapy sessions after week 1, we will troubleshoot any sticking points and retrain the therapist so that the CIMT flow is minimally interrupted by triggering taVNS. If the therapist is not able to achieve high fidelity scores of 3 on all items by week 2 of treating the first infant, we will have the BSL RA assist with all sessions to ensure CIMT delivery, and if funds exist, incorporate design changes to increase therapist efficiency with the taVNS system during CIMT.

Aim 2: To measure infant response to low-dosage 40h CIMT + active taVNS stimulation (n=5) in: 1) upper extremity motor abilities, 2) gross motor skills, 3) individual treatment goals before and at the end of CIMT treatment. We will assess motor skills at 3mo after completion of CIMT for maintenance of gains.

4.0 Study Endpoints

Aim 1: Primary CIMT feasibility outcomes: Ability of therapist to operate taVNS easily and successfully by earning a meeting or exceeding score (3 or 4) on random videotaped therapy sessions, as scored by CIMT fidelity treatment.

Aim 1: Primary taVNS safety and feasibility outcomes: Ability of infant to tolerate wired ear electrode and for electrode to remain securely in place with good contact with minor manipulation during sessions; <5% of sessions with sustained discomfort requiring decreasing current.

Aim 2: Primary Efficacy Outcome: We will use the Quality of Upper Extremity Skills Test (QUEST) subtests for grasp and dissociated movement as our primary outcome. The QUEST is a reliable, valid, quantitative outcome measure with excellent psychometric properties, and is recommended by NINDS/NICHD for the evaluation of movement patterns and hand function in children with cerebral palsy.⁴⁹ The subtests for grasp and dissociated movement have been used in published infant CIMT trials,⁸ and provide detailed information on hand function and quality of movement between the right and left sides of the body.

Aim 2: Secondary Efficacy Outcomes: We will use three other assessments for fine and gross motor function and meeting individual treatment goals: Developmental Assessment of Young Children (DAYC), the Gross Motor Function Measure-66 (GMFM-66) and the Goal Attainment Scale (GAS).

- The DAYC is a standardized assessment of early developmental skills from birth to 5 years of age⁵⁰ and is recommended for early detection of CP.⁵¹ We will use the DAYC Physical Development domain to assess developmentally appropriate fine and gross motor skills. [Mean (SD)=100±15 for each domain.]
- We will use the GMFM-66 as a comprehensive evaluation of foundational gross motor skills to assess how much of a task the infant can do rather than the quality of motor performance.^{48,52,53} Specific sections tested include Dimensions (A) Lying & rolling, (B) Sitting, (C) Crawling & kneeling, (D) Standing.^{52,53}
- The GAS is an individualized outcome measure that is standardized in order to calculate the extent to which a patient or group of patients' therapy goals are met.^{54,55} We will set individual goals for each infant and use the GAS scale to analyze differences between before and after CIMT+taVNS.

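### The primary endpoint on the therapist's operation of taVNS is judged only by a CIMT fidelity score, and it does not separate scores obtained with added research-assistant help

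*Combined protocol and SAP*

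**What the plan says.** **The endpoint.** Section 4.0 lists as the Aim 1 primary CIMT feasibility outcome: "Ability of therapist to operate taVNS easily and successfully by earning a meeting or exceeding score (3 or 4"), obtained on randomly chosen videotaped sessions scored for CIMT fidelity. No other criterion is attached to it.

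**The instrument.** The overview of innovation in Section 2.0 describes the purpose as "Assessment of therapist delivering CIMT with high fidelity using a CIMT fidelity tool". In Section 3.0, Aim 1, "a random weekly session (20% sessions) will be scored for CIMT treatment fidelity while the therapist is delivering taVNS". The tool is not reproduced, and no taVNS item is described.

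**The inference.** Section 3.0, Aim 1, states: "Scores that meet or exceed therapist goals indicate that taVNS can be delivered by the therapist while delivering high quality CIMT".

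**Who does what.** Section 3.0, Experimental set-up: "The therapist will activate a hand-held button for 2min-on/30 sec-off control of stimulation during a CIMT session". Step 5 of the Aim 1 procedures agrees: "The OT therapist delivering CIMT will start stimulation by pushing the button". Step 6 gives the RA one explicit in-session task. When contact is poor, "the BSL RA will adjust the electrode to ensure contact and delivery of stimulation".

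**Assistance.** Under Technical administration of taVNS, the RA both oversees and assists the stimulation at every session. Under Limitations and alternative approaches, RA help in most sessions after week 1 leads to troubleshooting and retraining. If the fidelity target is missed by week 2 of the first infant, RA assistance at all sessions becomes the remedy.

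**Ease of use.** Step 7 has the parent and the occupational therapist (OT) complete a weekly questionnaire "to assess their perception of ease of use, infant tolerance, general acceptance". Section 4.0 does not refer to it.

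**The concern.** The outcome is named for one thing (operating the device) and scored on another (the quality of CIMT). The fallback assistance is introduced to protect CIMT delivery, which is the quantity being scored. It could therefore raise the score in just the situation where the therapist found it hard to combine the two tasks. If the endpoint were then reported in the words of Section 4.0, a result that depended on a second trained person could be presented as therapist operability.

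This matters because feasibility is the main product of the pilot. Section 1.0 presents it as the step before an NIH application, and Section 2.0 links therapist control of the device to eventual home-based use. Whether a second person is needed bears directly on that plan.

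**Working it through.** **Step 1. Reproduce the plan's own figures.** Inputs from Section 3.0: 5 sessions a week, 4 weeks, 2 hours each, one randomly chosen session scored per week. Inputs from Section 6.0: up to 10 infants, at least 5 completed courses.

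- Sessions per infant: 5 × 4 = 20. Hours: 20 × 2 = 40, as stated.
- Share scored: 1 of 5 per week = 20%, as stated. Scored per infant: 0.20 × 20 = 4.
- 5 completed courses: 5 × 4 = 20 scored of 5 × 20 = 100.
- 10 completed courses: 10 × 4 = 40 scored of 10 × 20 = 200.

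The plan's figures are internally consistent. The issue is what the score can show, not a numerical error.

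**Step 2. Set the stated purposes of the score side by side.**

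| Place | What the score is said to show | Can a CIMT fidelity score alone show it? |
|---|---|---|
| 1.0, Aim 1 | taVNS delivery does not detract from CIMT quality | Yes for CIMT quality; therapist delivery is presumed |
| 10.0 | CIMT fidelity during therapist-delivered taVNS | Yes for fidelity; therapist delivery is presumed |
| 3.0, Aim 1 | The therapist can deliver taVNS while CIMT stays high quality | Second half only |
| 4.0 | The therapist operates taVNS easily and successfully | No |

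The other Aim 1 primary outcome in Section 4.0 concerns infant tolerance, electrode contact and discomfort, so it does not supply the missing criterion.

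**Step 3. Place the assistance rules against the endpoint.** Assistance is routine at every session in one paragraph of Section 3.0. In another it is a warning sign after week 1 and then a remedy. The word is not defined, so supervision, set-up, electrode adjustment and pressing the trigger are not told apart. Section 4.0 does not say how scores from sessions with added help enter the endpoint.

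**Step 4. How many scored sessions could fall after the fallback?** At one scored session a week, at most 2 of the first infant's 4 scored sessions exist by the end of week 2. There could be fewer, because no scoring turnaround is given. Assume the fallback starts after week 2. Whether it carries over to later infants is not stated, so both cases are shown:

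| Assumption | 5 infants | 10 infants |
|---|---|---|
| First infant only | 2/20 = 10% | 2/40 = 5% |
| Rest of the study | (20 − 2)/20 = 18/20 = 90% | (40 − 2)/40 = 38/40 = 95% |

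These are scored sessions with added RA assistance of an undefined kind. They are not sessions in which the RA operated the trigger, and that number cannot be derived from the documents. The table applies only if the fallback is set off at all.

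**The case against.** The strongest reply is that Section 4.0 labels this outcome as CIMT feasibility, and that Sections 1.0 and 10.0 frame the question as whether CIMT quality survives while the therapist runs taVNS. A CIMT fidelity tool suits that question. On this reading the mismatch is loose wording in Section 4.0. Most of this stands, and it is why the remedy is largely rewording. It does not remove the point: the Section 4.0 wording is the definition of a primary outcome, and Section 3.0 draws the same inference about delivery by the therapist.

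Other replies also carry weight. Heavy assistance is openly treated as a problem, and needing the fallback would itself be a reportable feasibility finding. Ease of use is collected weekly from the OT; it is missing from the endpoint, not from the study. The fidelity tool is not reproduced, so an added taVNS item cannot be ruled out.

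Three stronger readings are tempting, and the documents do not support them:

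- *The RA would in practice run the device.* The trigger is assigned to the therapist in the set-up and in step 5, and nowhere is the RA said to press it. The RA is trained to deliver stimulation, so it is possible, but it is not planned.
- *Passing scores with RA help would count the same as unaided ones.* The plan is silent on this, and silence does not establish a counting rule.
- *Nobody could tell who operated the trigger.* Sessions are videotaped, so it may be checkable. What is missing is an instruction to record it.

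A rule that fails any session in which the RA touched the trigger would also go too far. With a 2.5-minute cycle, a 2-hour session has room for up to 120 / 2.5 = 48 cycles, and one RA press would void an otherwise therapist-run session.

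**Conclusion.** The point holds in limited form. The only criterion for the Section 4.0 outcome supports a claim about CIMT quality during taVNS. It does not by itself support a claim that the therapist operated the device easily or unaided. Because added RA help is not separated in the endpoint, the outcome could be met with that support and still be read as therapist operability.

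The evidence at issue is 20 to 40 scored sessions of 100 to 200, assuming 5 to 10 completed courses at 4 scored sessions each. The share obtained after the fallback could range from none to 95%, depending on whether it is set off and how long it lasts. The frequency of RA trigger operation is unknown. The conclusion also assumes that the unseen fidelity tool has no taVNS item, as its descriptions suggest. Severity is minor to moderate and confidence is moderate. No treatment procedure or numerical result is called into question.

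**What to change.** 1. **Reword the claim.** In the Section 4.0 endpoint and the Section 3.0 inference, state the conclusion as: *CIMT fidelity is maintained while the therapist delivers taVNS with RA supervision and assistance.*
2. **Define assistance and record it.** Give *assist* one meaning, so that the Technical administration and Limitations paragraphs of Section 3.0 agree. Separate supervision, set-up and electrode adjustment from operating the trigger. Have the RA, who is already present, record for each session whether the RA operated the trigger. This can be checked on the videos already being scored.
3. **Report by assistance.** Give the share of scored sessions at 3 or 4 separately with and without RA trigger operation, and before and after any fallback. Base any claim of independent therapist operation only on sessions without RA trigger operation. Report the weekly OT ease-of-use answers as the evidence on ease.

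The cost is one field per session, so 100 to 200 short entries, with checks possible on the 20 to 40 videos already scored. The therapist records nothing extra. The drawback is a possibly weaker feasibility claim. The field should be in place before the first infant is treated, because only a fifth of sessions are planned to be scored from video.
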